6.7.7. Reproductive Risk/Pregnancy

As stated in the study inclusion criteria ([Section 4.1](#)), female patients of childbearing potential enrolled in this study must agree to use a medically acceptable method of contraception ([Section 4.3](#)) from Screening, throughout the entire study period, and for 30 days after the patient's last dose of the last course of RC-P. Medically acceptable methods of contraception that may be used by the male partner of a female patient are condom and spermicide (or adequate and approved alternatives) or vasectomy (> 6 months prior to Day -1). Male patients enrolled in this study agree to refrain from sperm donation for 30 days after the patient completes the study and to use adequate contraception (as described above) throughout the entire study period and for 30 days after the patient's last dose of the last course of RC-P.

If a patient or a male patient's partner becomes pregnant any time after study drug dosing until 30 days after study drug dosing, the pregnancy must be reported within 24 hours of first knowledge of the event by study site personnel. RC-P must be stopped for any pregnant subject (see [Section 6.8.1](#)). The Pregnancy Reporting Form should be used to report the pregnancy. The pregnancy of a patient or a male patient's partner (once informed consent is signed) must be followed until the outcome of the pregnancy is known, and in the case of a live birth, for 6 months following the birth of the child. The Infant Follow-up Form should be used to report information regarding the status of the infant.

The Pregnancy Report Form, Infant Follow-up Form, and contact information for submission of the form, will be provided to the study sites separately.

6.7.8. Regulatory Reporting

Jazz Pharmaceuticals or its designee is responsible for reporting relevant SAEs to the relevant regulatory authorities, concerned Central Ethics Committees (CECs) and participating Investigators, in accordance with ICH guidelines, the US Code of Federal Regulations (CFR), the EU Clinical Trial Directive (2001/20/EC) and/or local regulatory requirements.

The reference safety information to determine expectedness of RC-P treatment-emergent SAEs is specified in the [RC-P IB](#).

Suspected unexpected serious adverse reactions (SUSARs) will be reported to the relevant regulatory authorities, CECs, and participating Investigators no later than 15 days after first knowledge of the event.

SUSARs that are fatal or life-threatening will be reported to the relevant regulatory authorities and CECs no later than 7 days after knowledge of such a case, and relevant follow-up information provided within an additional 8 days.

Once a year throughout the clinical study, a report listing of all SUSARs (and SAEs if required by local regulation) that have occurred during this period and a report of the patient's safety will be submitted to the applicable authorities, and as otherwise required by local laws.

Reporting of SAEs by the Investigator to his/her local ethics committee will be done in accordance with the standard operating procedures and policies of the ethics committee. Adequate documentation must be maintained showing that the IRB/REB/IEC was properly notified.

The events listed below will NOT be reported to FDA expeditiously as Investigational New Drug (IND) individual case safety reports unless fatal or life-threatening. These events will be reported to FDA as IND safety reports only if aggregate analysis by Jazz indicates that the event is occurring more frequently than anticipated.

Events that are commonly reported as asparaginase-related toxicities in pediatric patients (Raetz & Salzer 2010)

Allergic reaction (including hypersensitivity and anaphylactic reaction)

Pancreatitis

Thrombosis

Hyperglycemia

Events that are common in the study population

Fever (including febrile neutropenia)

Infections (including bacterial, fungal, and viral)

Hemorrhage

Nausea/Vomiting

6.8. Removal of Patients from the Study or Study Drug

6.8.1. Patient Withdrawal

Patients may withdraw from the study at any time at their own request, or they may be withdrawn at any time at the discretion of the Investigator or Jazz Pharmaceuticals or its designee at any time for any reason.

In accordance with the ICH principles of GCP, the Investigator may advise a patient to withdraw from the study if the patient's safety or well-being is compromised by his or her further participation in study. Other reasons for withdrawal may include the following:

- Patient withdraws consent
- Death

-
- Adverse event which in the opinion of the Investigator contraindicates continuation in the study
 - Noncompliance with study drug
 - Investigator considers it not in the patient's best interest to continue in the study
 - Pregnancy
 - Jazz Pharmaceuticals (or its designee) decision to terminate study

For all patients who prematurely discontinue the study, an attempt should be made to perform all discharge safety follow-up assessments 30 days after the last dose for the last course of RC-P. If the patient refuses to complete all of the 30-day safety follow up assessments, then as many assessments as possible should be completed; at a minimum the AE review.

The specific reason for the discontinuation should be carefully documented. If a patient withdraws informed consent, the specific reason for withdrawing the informed consent should be stated.

Adverse events resulting in discontinuation of study drug or study termination should be followed for as long as necessary to adequately evaluate the patient's safety, or until the event stabilizes, or the patient is lost to follow up. If the event resolves during the study, a resolution date should be recorded, for both AEs and SAEs. If at the time of the final scheduled study visit, the AE resulting in discontinuation of study drug or study termination is not resolved, the outcome at that time should be recorded. Once the final outcome is determined for an SAE this information should be provided as follow-up SAE information.

To ensure sufficient numbers of evaluable patients are available with PK data, additional patients may be enrolled as necessary upon agreement of the Investigator and Sponsor.

6.8.2. Sponsor's Termination of the Study

Jazz Pharmaceuticals reserves the right to discontinue the study at any time for any reason. Such a termination must be implemented by the Investigator, if instructed to do so by Jazz Pharmaceuticals, in a time frame that is compatible with the patients' well-being.

The Sponsor may determine to discontinue an arm of the study within a cohort or a complete cohort based on the efficacy and safety/tolerability results ([Section 3.1.3](#)).

6.9. Appropriateness of Measurements

The PK blood sampling and analyses for this study are considered sufficient to characterize the SAA-time profiles. The parameters (monitoring of AEs, clinical laboratory tests, vital signs, and physical examinations) selected to assess the safety of each of these study drugs are appropriate since they are routinely used to assess the safety profile of drugs in clinical studies.

7. STUDY ACTIVITIES

Study procedures and assessments are provided in [Section 6](#) with the timing presented in [Appendix 1](#); the PK and PD sampling schedule for IM RC-P and IV RC-P patients is in [Appendix 2](#).

8. PLANNED STATISTICAL ANALYSIS

8.1. General Considerations

Data from the study will be summarized by dose level for both IM RC-P (Part A) and IV RC-P (Part B) patients in general. Categorical variables (eg, sex, race, etc.) will be reported using frequency and percentage. Continuous variables (eg, age, weight, etc.) will be reported using the number of patients (n), mean, standard deviation, median, minimum, and maximum. All summaries, statistical analyses, and individual patient data listings described below will be completed using Version 9.4 or later of the Statistical Analysis System (SAS Institute, Inc. Cary, NC).

8.2. Treatment Assignments

Patients in Part A will be allocated IM RC-P and patients in Part B will be allocated IV RC-P as described in [Section 5.6](#).

8.3. Determination of Sample Size

For Part A (RC-P by IM administration, Cohorts 1 and 2) of the study, 98 patients administered the final IM dose level are planned.

For the final IM RC-P dose level, 13 evaluable patients are planned in Part A Cohort 1 (IM RC-P Dose Confirmation), and approximately 85 patients are planned in Cohort 2 (IM Expansion) to obtain 98 patients in total at the final dose in Part A for the primary efficacy analysis of the IM administration route.

The sample size of 13 evaluable patients in Part A Cohort 1 provides at least 80% posterior probability of the true response rate $\geq 96\%$ given 100% response rate in Cohort 1 and non-informative neutral beta prior with $\alpha=\beta=1/3$.

Since the primary efficacy endpoint is considered to be met if the lower bound of the 95% Wald CI of the response rate exceeds 90%, the final sample size is planned as 98 patients which provides 83% probability that the lower bound of the 95% Wald CI exceeds 90%, assuming a true response rate of 96% for the primary efficacy endpoint and a 5% drop out rate. Furthermore, with a sample size of 98 patients, the probability of observing at least one AE related to asparaginase with an incidence as low as 3% is 95%.

For the primary efficacy assessment at the primary analysis, a minimum of 93 patients in the Efficacy Analysis Set are required. This means at least 93 patients received at least one dose of the final IM RC-P dose level, and had at least one 72-hour NSAA assessment collected within the protocol-defined sample collection window (± 2 hours) in Course 1. If fewer than 93 out of 98 patients have the necessary data, additional patients will be enrolled to ensure 93 patients for analysis.

One interim analysis with 51 patients is planned. At the interim analysis, a sample size of 51 patients provides 70% probability that the lower bound of the 95% CI exceeds 90% under the assumption of a 96% true response rate and a 5% drop out rate. The probability of observing at least one AE related to asparaginase with an incidence as low as 3% is 79% with 51 patients.

Similar to the primary analysis, a minimum of 48 patients in the Efficacy Analysis Set for the primary efficacy assessment are necessary for the interim analysis. If fewer than 48 out of

51 patients have the necessary data, additional patients will be enrolled to ensure 48 patients for analysis.

The probability of the lower bound of the 95% CI exceeds 90% will be less than 80% with a sample size of 98 patients if the true response rate is less than 96%. For example, if the true response rate is 94% for the primary efficacy endpoint, with a 5% drop out rate, a sample size of 98 patients provides 51% probability that the lower bound of the 95% CI exceeds 90%.

For Part B (RC-P by IV administration, Cohort 1), a target of at least 6 evaluable patients will be administered the first IV dose level. This sample size is not based on formal power calculation but provides an initial assessment of the IV RC-P dosing.

8.4. Analysis Sets and Handling of Dropouts

- Enrolled Analysis Set will include patients who signed the informed consent and meet inclusion/exclusion criteria per Investigator
- Safety Analysis Set will include patients who received at least one dose of RC-P
- Efficacy Analysis Set will include patients who received at least one dose of RC-P and have at least one 48- or 72-hour NSAA assessment collected within the protocol-defined sample collection window (± 2 hours) in Course 1
- PK Analysis Set will include patients who received at least one dose of RC-P and have at least one postdose evaluable SAA or PK concentration value
- PD Analysis Set will include patients who received at least one dose of RC-P and have at least one postdose evaluable L-asparagine or L-glutamine value

8.5. Handling of Missing Data

In general, missing data will be treated as missing completely at random and will not be imputed. Handling of missing PK concentrations and PK concentrations that are below the limit of quantitation (BLQ) will be described in the statistical analysis plan (SAP).

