8.7. Efficacy Analyses

8.7.1. Primary Efficacy Endpoint and Analysis

The primary efficacy endpoint of the study is the response rate, defined as the proportion of patients with the last 72-hour NSAA level ≥ 0.1 IU/mL during the first course of IM administration of RC-P. Patients in both Part A Cohort 1 and Cohort 2 at the final IM RC-P dose level will be included. Depending on the RC-P start day for a patient, this could be predose 4 if

the first course of RC-P started on a Monday; predose 6 if the first course of RC-P started on a Wednesday; or predose 5 if the first course of RC-P started on a Friday.

The primary efficacy endpoint will be estimated using the Efficacy Analysis Set for patients administered the final IM RC-P dose level with at least one 72-hour NSAA assessment collected within the protocol-defined sample collection window (± 2 hours) in Course 1 of Part A. The last observed 72-hour NSAA assessment collected within the protocol-defined sample collection window (± 2 hours) in Course 1 will be used in the calculation of the primary efficacy endpoint. Missing data will not be imputed. The response rate, along with the 95% Wald CI (confidence interval) will be provided. The primary efficacy endpoint will be met if the lower bound of the 95% CI of the response rate exceeds 90%.

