## 5.3. Power and Sample Size Considerations

For Part A of the study, 98 patients administered the final IM dose level are planned.

For the final IM RC-P dose level, 13 evaluable patients are planned in Part A Cohort 1 (IM RC-P Dose Confirmation), and approximately 85 patients are planned in Cohort 2 (IM Expansion) to obtain 98 patients in total at the final dose in Part A for the primary efficacy analysis of the IM administration route.

The sample size of 13 evaluable patients in Part A Cohort 1 provides at least 80% posterior probability of the true response rate  $\geq 96\%$  given 100% response rate in Cohort 1 and non-informative neutral beta prior with  $\alpha = \beta = 1/3$ .

Since the primary efficacy endpoint is considered to be met if the lower bound of the 95% Wald confidence interval (CI) of the response rate exceeds 90%, the final sample size is planned as 98 patients which provides 83% probability that the lower bound of the 95% Wald CI exceeds 90%, assuming a true response rate of 96% for the primary efficacy endpoint and a 5% drop out rate. Furthermore, with a sample size of 98 patients, the probability of observing at least one adverse events (AE) related to asparaginase with an incidence as low as 3% is 95%.

For the primary efficacy assessment at the primary analysis, a minimum of 93 patients in the Efficacy Analysis Set are required. This means at least 93 patients received at least one dose of the final IM RC-P dose level, and had at least one 72-hour NSAA assessment collected within the protocol-defined sample collection window ( $\pm 2$  hours) in Course 1. If fewer than 93 out of 98 patients have the necessary data, additional patients will be enrolled to ensure 93 patients for analysis.

One interim analysis with 51 patients is planned. At the interim analysis, a sample size of 51 patients provides 70% probability that the lower bound of the 95% CI exceeds 90% under the assumption of a 96% true response rate and a 5% drop out rate. The probability of observing at least one AE related to asparaginase with an incidence as low as 3% is 79% with 51 patients.

Similar to the primary analysis, a minimum of 48 patients in the Efficacy Analysis Set for the primary efficacy assessment are necessary for the interim analysis. If fewer than 48 out of 51 patients have the necessary data, additional patients will be enrolled to ensure 48 patients for analysis.

Jazz Pharmaceuticals Ireland Limited  

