#### 7.2.5. Missing and Partial Data

Any missing AE information such as severity and relationship will be handled as described in [Section 10.2](#) and [Appendix I](#).

Missing PK levels will be handled as described in [Section 11](#).

Jazz Pharmaceuticals Ireland Limited  
Statistical Analysis Plan – Protocol JZP458-201

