#### **9.1.2. Analysis of the Primary Efficacy Endpoint**

The primary efficacy endpoint will be estimated using the Efficacy Analysis Set for patients administered the final IM RC-P dose level with at least one 72-hour NSAA assessment collected within the protocol defined sample collection window ( $\pm 2$  hours) in Course 1 of Part A. The last observed 72-hour NSAA assessment collected within the protocol defined sample collection window ( $\pm 2$  hours) in Course 1 will be used in the calculation of the primary efficacy endpoint. Missing data will not be imputed. The response rate, along with the 95% Wald CI will be provided. The primary efficacy endpoint will be met if the lower bound of the 95% CI of the response rate exceeds 90%.

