## 11. PHARMACOKINETIC/PHARMACODYNAMIC ANALYSES

The summary and listings of RC-P PK (SAA and serum asparaginase concentration levels) and PD (asparagine and glutamine concentrations) measurements will be provided. Descriptive statistics including number of patients, mean, SD, median, min, max, coefficient of variation (CV), geometric mean, and geometric standard deviation will be used to summarize PK and PD data by time, dose level, Course, and route of administration (IM or IV), as appropriate. Proportion of patients with NSAA  $\geq 0.1$  and  $\geq 0.4$  IU/mL by time will also be summarized for SAA data.

Individual and/or summary figures of SAA-time or enzyme concentration-time profiles in serum may be provided. Individual and/or summary figures of SAA versus PD profiles may also be provided.

Statistical summaries and displays will be based on scheduled sampling times unless significant deviations occur (outside of the specified time windows in Appendix 2 in protocol). Differences between scheduled and actual sampling times will be listed for all patients.

RC-P SAA data will be used in a population PK analysis. A population PK model will be used to characterize the RC-P PK profiles in patients with ALL/LBL following hypersensitivity to *E. coli*-derived asparaginases, and to explore exposure-response correlations. Results from the population PK analysis will be reported separately from the CSR, in a standalone document.

Jazz Pharmaceuticals Ireland Limited  
Statistical Analysis Plan – Protocol JZP458-201

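### No planned analysis returns treated patients without an in-window 72-hour NSAA to the primary response rate; at the minimum analysed sets, a few excluded failures could reverse a met endpoint

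*Protocol*

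**What the plan says.** Protocol 8.7.1 restricts the primary estimate to "patients administered the final IM RC-P dose level with at least one 72-hour NSAA assessment collected within the protocol-defined sample collection window" in Course 1 of Part A. SAP 9.1.2 repeats the restriction and adds "Missing data will not be imputed". The general rule in protocol 8.5 is "In general, missing data will be treated as missing completely at random and will not be imputed".

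The endpoint is met if the lower bound of the 95% Wald interval exceeds 90%. The plan sets minimum analysed numbers and replaces patients to reach them. For the primary analysis, SAP 5.3 says: "If fewer than 93 out of 98 patients have the necessary data, additional patients will be enrolled to ensure 93 patients for analysis". The interim has the parallel condition "If fewer than 48 out of 51 patients have the necessary data", with enrolment continuing until 48 are available. No upper limit on the number left out is stated.

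The only sensitivity analysis of the primary endpoint (SAP 9.1.3) excludes patients who missed Course 1 PK samples because of COVID-19.

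Protocol 8.5 also says: "Handling of missing PK concentrations and PK concentrations that are below the limit of quantitation (BLQ) will be described in the statistical analysis plan". SAP 7.2.5 reads "Missing PK levels will be handled as described in" Section 11. Section 11 deals with sampling-time deviations ("Statistical summaries and displays will be based on scheduled sampling times unless significant deviations occur") and gives no rule for missing levels.

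**The concern.** Leaving patients out is harmless if the reason for the missing sample has nothing to do with outcome. Here it can. Protocol 5.5.1 discontinues RC-P for a Grade 3 or worse allergic reaction, and protocol 1.1 notes that antibodies to asparaginases may interfere with the enzyme's effect. Under the sampling schedule in protocol Appendix 2, a Monday starter has the first 72-hour sample after dose 3, and a Wednesday starter after dose 2. A Monday starter who stops before dose 3, or a Wednesday starter who stops before dose 2, has no scheduled 72-hour sample and leaves the denominator. A Friday starter has a 72-hour sample after dose 1, so a stopper can still be scored.

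At stake is how a met endpoint is read. Protocol 3.2 calls the study pivotal, success turns on one threshold, and meeting it at the interim stops enrolment. If the lower bound clears 90% by one or two patients, a reader will ask whether it would still do so with the excluded patients counted. No pre-specified analysis answers that.

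**Working it through.** **Inputs.** Success rule: 95% Wald lower bound above 0.90 (protocol 8.7.1). Minimum analysed: 93 of 98, and 48 of 51 at the interim, so at most 5 and 3 treated patients are left out before replacement (SAP 5.3). Planning rate: 96%. The number of failures among excluded patients is not in the documents, so it is varied.

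**Formula.** LB(x, n) = p − 1.96·√(p(1−p)/n), with p = x/n.

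**Step 1: reproduce the plan's figures.**
- n = 93: LB(88, 93) = 0.9004 passes and LB(87, 93) = 0.8856 fails, so 88 responders are needed. P(X ≥ 88 | 93, 0.96) = 0.831, matching the stated 83%. At 94% it is 0.512, matching the stated 51%.
- n = 48: LB(46, 48) = 0.9018 passes and LB(45, 48) = 0.8690 fails, so 46 are needed. P(X ≥ 46 | 48, 0.96) = 0.699, matching the stated 70%.

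**Step 2: add k excluded patients as failures.** Hold x fixed and find the smallest k for which LB(x, n + k) is at or below 0.90. The last column is each result's share of all passing results at a true rate of 96%.

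| Result | Last pass | First fail | k to reverse | Share of passing results |
|---|---|---|---|---|
| 88/93 | 88/93, 0.9004 | 88/94, 0.8868 | 1 | 17.6% |
| 89/93 | 89/94, 0.9014 | 89/95, 0.8879 | 2 | 23.8% |
| 90/93 | 90/95, 0.9025 | 90/96, 0.8891 | 3 | 25.4% |
| 91/93 | 91/96, 0.9035 | 91/97, 0.8902 | 4 | 20.1% |
| 92/93 | 92/97, 0.9045 | 92/98, 0.8913 | 5 | 10.5% |
| 93/93 | 93/98, 0.9054 | 93/99, 0.8924 | 6 | 2.7% |
| 46/48 | 46/48, 0.9018 | 46/49, 0.8716 | 1 | 39.5% |
| 47/48 | 47/49, 0.9038 | 47/50, 0.8742 | 2 | 40.3% |
| 48/48 | 48/50, 0.9057 | 48/51, 0.8766 | 3 | 20.2% |

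**Step 3: accumulate the shares.**
- One excluded failure reverses 17.6% of passing final results and 39.5% of passing interim results.
- Two reverse 17.6 + 23.8 = 41.4% and 39.5 + 40.3 = 79.8%.
- Three reverse 41.4 + 25.4 = 66.8% of final results and all interim results.

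**Step 4: relax the minimum.** With all 98 in the denominator, 93 responders are needed (93/98: 0.9054; 92/98: 0.8913). With 95 of 98 analysed, the passing results are 90 to 95. Three excluded failures reverse 90, 91 and 92, while 93, 94 and 95 stand. With 97 analysed, the one excluded patient can reverse only 92/97.

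**The case against.** **Any threshold rule tips at its minimum pass.** True. The table is a worst case: reversing 92/93 needs all five excluded patients to be failures, and reversing 48/48 needs all three. A reader might infer that nearly every passing result is fragile. The documents do not support that. The counts hold only at exactly 93 or 48 analysed, more analysed patients leave fewer to exclude, and nothing in the plan leads one to expect three or more excluded failures. The structurally excluded stoppers are also a narrow group.

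**The exclusions are not hidden.** This largely stands. SAP 8.2 tabulates the analysis sets, summarises reasons for stopping study drug, and lists each patient's analysis set and completion status. SAP 11 gives the proportion with NSAA ≥ 0.1 IU/mL by time. An excluded patient with an in-window 48-hour sample still counts in the key secondary endpoint, and allergic reactions appear in the AE tables. A reader could do the tipping arithmetic from the reported counts. Even so, none of these outputs is a 72-hour response rate that includes the excluded patients.

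**It is an estimand choice.** The endpoint is measured activity in observed samples, and counting a stopper as a failure assumes what was not measured. That stands, and it is why the added analysis should be supplementary.

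**The missing-data cross-reference.** A reader might infer that the gap between SAP 7.2.5 and Section 11 leaves the primary analysis undefined. It does not: SAP 9.1.2 states its own no-imputation rule, so the gap cannot change the primary result.

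**Conclusion.** The point holds as a cheap improvement. Treated final-dose IM patients without an in-window 72-hour NSAA leave the primary rate, some of them possibly for treatment-related reasons, and no planned analysis counts them in that rate.

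The size is a tipping range. It rests on the minimum analysed sets, on every added patient being a failure and, for the shares, on a true rate of 96%. One excluded failure is enough only for the narrowest pass, 88/93 or 46/48. Within five exclusions 93/93 cannot be reversed; because replacement has no stated limit, a sixth exclusion is possible.

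A reader might go further and conclude that the primary estimate is biased upwards. The documents do not show this. They give neither the number of exclusions to expect nor the failure rate among them, and many missed samples may be logistic.

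**What to change.** Keep the primary and COVID-19 analyses unchanged. In SAP 9.1.3 add:

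1. One pre-specified supplementary analysis on all patients treated at the final IM dose in Part A. Patients with no in-window 72-hour NSAA in Course 1 count as non-responders, and the same 95% Wald interval is reported.
2. A tipping-point table over those patients, showing how many would have to be failures for the lower bound to fall to 90% or below. Set beside it their study-drug discontinuation status and reason, which SAP 8.2 already summarises. Reasons for missed samples should not be assumed available, since SAP 13 describes capturing them only for COVID-19.

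Optionally, repeat the first analysis with Course 1 stoppers who have only a first-half 72-hour sample also counted as non-responders. These are patients whose only such sample is predose 3 after a Wednesday start or predose 2 after a Friday start. Label this an alternative estimand, because it overrides an observed value.

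The cost is a paragraph of SAP text, one estimate and one table, with no extra patients or samples. The downside is that the supplementary estimate is conservative: it counts logistic misses as failures and can only equal the primary or be less favourable.
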